11. ETHICAL CONSIDERATIONS.....	34
12. INSURANCE AND INDEMNITY.....	34
13. FUNDING	34
14. ANNUAL REPORTS	35
15. REFERENCES.....	35
APPENDIX A: DiRECT-Aus SCHEDULE OF ASSESSMENTS.....	38

Summary

Study title: **Diabetes REmission Clinical Trial-Australia - DiRECT- Aus Study**

Protocol version 3.0

Objectives Primary objective

To determine whether a program, designed to achieve remission of T2DM to normal glucose tolerance by substantial weight loss using a very low energy diet (VLED), can be effectively delivered within the routine primary care setting where most people with T2DM are managed.

Secondary objectives

To evaluate the attitudes of participants to the very low energy diet (VLED) program including acceptability, ease of use and perceived value.

Study design

DiRECT-Aus is a translational study based on the active arm of the DiRECT trial (UK) which demonstrated effectiveness in achieving remission of T2DM using a structured weight management program in primary care.

Planned sample size

250 subjects recruited from 5 Primary Health Networks (PHNs) through 5 general practitioner (GP) practices per PHN (total 50 GP practices recruiting 10 subjects per practice).

Selection criteria

- Men and women aged 20-65 years, all ethnicities
- Type 2 Diabetes Mellitus of duration 0-6 years
- Body mass index (BMI)>27 kg/m²

Study procedure

GP Practices will deliver an VLED phase followed by structured food reintroduction and long term weight loss maintenance. Training for the practice nurses/dietitians in VLED delivery, maintenance diet program and behaviour therapy will be provided by the Metabolism & Obesity Services, Royal Prince Alfred Hospital and Boden Collaboration, University of Sydney

Statistical considerations

The objective of the study is to determine if a VLED and structured weight management program can be instituted as effectively in primary care in Australia as in the original UK DiRECT trial.

Duration of the Study - Active intervention: 12 months per subject. Follow up: 4 years after completion of active intervention (subject to funding)

ABBREVIATIONS

App	Appendix
Appt	Appointment
BMI	Body Mass Index
CHD	Coronary Heart Disease
eGFR	Estimated Glomerular Filtration Rate
GP	General Practitioner
ITT	Intention to Treat
LED	Low Energy Diet
VLED	Very Low Energy Diet
SLHD	Sydney Local Health District
OHA	Oral Hypoglycaemic Agent
PHN	Primary Health Network
RCT	Randomised Controlled Trial
T2DM	Type 2 Diabetes Mellitus
TDR	Total Diet Replacement
GIG	Governance and implementation Group

STUDY SYNOPSIS

[figure not shown]
Title of Study:	Diabetes REmission Clinical Trial-Aus; DiRECT-Aus
Study Centre:	University of Sydney
Duration of Study:	Active intervention: 12 month per subject Follow up: 4 years after completion of active intervention
Primary Objective:	
To determine whether a program, designed to achieve remission of T2DM to normal glucose tolerance by substantial weight loss using a very low energy diet (VLED), can be effectively delivered within the routine primary care setting where most people with T2DM are managed in Australia.
 
The Diabetes Remission Clinical Trial (DiRECT) was a study funded by Diabetes UK that tested whether a low calorie-based weight management program, delivered in primary care could result in long term Type 2 diabetes remission. Diabetes UK, the University of Glasgow and Newcastle University have since developed the DiRECT principles, which set out the core elements of health intervention to have the best chance of replicating the outcomes of the DiRECT study.
 
This project intent is to replicate or better the remission results achieved in the UK DiRECT study for people with T2DM in the participating PHN regions and undertaking the intervention in general practice.

Secondary Objective:	To evaluate the attitudes of participants to the VLED program including acceptability, ease of use and perceived value.
Primary Endpoint:	% of participants achieving a non-diabetic HbA1c (<6.5%; <48 mmol/mol) at 12 months having ceased all diabetes medication for at least the preceding 2 months
Rationale:	Bariatric surgery can convert 70-80% of people with T2DM to the non-diabetic state. The DiRECT trial provided evidence that T2DM could also be reversed by a strict energy restricted diet, with 10-15kg weight loss. The present study will determine if the results of the DiRECT trial can be replicated in an Australian primary care setting and establish whether it is possible to produce remission of T2DM at 12 months and sustain it over 5 years. An VLED can be provided relatively cheaply in the primary care setting where obesity and T2DM are managed, using a total diet replacement (TDR), such as Optifast, which is readily available to the Australian general public. The study will also assess quality of life and attitudes of subjects during the intervention.

Methodology:	
The study will be 'realistic' to ensure transferability into routine care and will be set within primary care where T2DM is managed.
 
Consenting general practices within 5 Primary Health Networks (PHNs) in NSW will participate in delivering the intervention, which is a weight management program that includes a TDR phase, followed by structured food reintroduction and long-term weight loss maintenance. To increase access in regional areas, the intervention may be delivered via telehealth but all participants will attend their GP practice for safety monitoring and collection of study data.
 
Participants will otherwise continue to be managed as usual, following current guidelines.

Sample Size:	250 subjects recruited from 5 PHNs through 5 GP practices per PHN (total 25 GP practices recruiting 10 subjects per practice).
Screening:	Potential participants will be identified by GPs either as part of routine care or a search of patient records in participating GP practices. GPs may request the assistance of researchers at Diabetes NSW & ACT with recruitment which will entail sending of invitation letters to potential participants and discussing the study with potential participants over the telephone. Potential participants will have access to a toll-free phone number monitored by Diabetes NSW & ACT and a study website for more information about the study. A study poster, brochure and Information Pack will also be available in participating GP practices.
Main Inclusion Criteria:	
 • Men and women aged 20-65 years, all ethnicities • T2DM of duration 0-6 years • Body mass index (BMI)>27 kg/m²
Main Exclusion Criteria:	
 • Current insulin use • HbA1c ≥ 86 mmol/mol (10%) at screening • eGFR ≤ 45 ml/min/1.73² at screening • Severe or unstable heart failure (≥ New York Heart Association class 3) • Patients with unstable mental illness 
Substance abuse
 
 • Substance abuse • History of active or untreated malignancy or in remission from a clinically significant malignancy for less than 5 years. Exceptions to this criterion include basal or squamous cell skin cancer, in situ carcinoma of the cervix or in situ prostatic cancer

	
 • Myocardial infarction within previous 6 months • Learning difficulties which in the opinion of the investigator prevent the subject providing informed consent and complying safely with the diet • Use of weight loss agents or medications taken to primarily reduce weight (eg orlistat, lorcaserin, Qysmia, Contrave, GLP-1 receptor analogues, over the counter or herbal weight loss agents) within the past 3 months • Have ever been diagnosed with and eating disorder or engaged in purging behaviour • Pregnant/ considering pregnancy • people currently participating in another clinical research trial • Allergy to Optifast or any of its ingredients
Product, Dose, Modes of Administration:	
The intervention is a 3400kJ (800kcal)/day TDR, followed for 13 weeks, with stepped food reintroduction to long-term weight loss maintenance using a tested energy-restricted nutritionally balanced (30% fat, < 10% saturated fat) maintenance diet using food-group exchanges, and support for behaviour change. Physical activity will be encouraged with a recommendation of at least 30 minutes brisk-walking daily and aiming to reach and maintain an individual sustainable maximum with a target of 15,000 steps/day.
 
Participants will continue to receive standard care under current clinical guidelines for T2DM. Intention to treat analysis will be conducted, with follow-up data continuing to be collected even if treatment is stopped.
 
The intervention will be delivered in primary care practices by practice nurses/dietitians (according to local availability and practice) with training, support and mentoring from the Boden Collaboration, University of Sydney.

Duration of Treatment:	12 months. Subject to additional funding, at least annual follow up for 5 years
Statistical Analysis:	
Data will be analysed primarily on an intention-to-treat (ITT) basis, using last observation carried forward for weight and diabetes status for subjects who discontinue the formal weight management program or experience an adverse event.
 
A ‘completers analysis’ of participants who complete the study will also be performed.

STUDY FLOW CHART

Screening and Baseline appointments

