3.5 Withdrawal of subjects

Patients who withdraw from the study after commencement of participation in the study will continue to have data collected from their routine GP visits, unless they specifically withdraw consent for this. Data on weight and HbA1c recorded in GP notes within 3 months either side of the patients planned 12 months follow-up date will be used. Data analysis will use best available follow-up weights (from routine attendances) and end of study diabetes status for subjects who discontinue the formal weight management program.

Diet intolerance or poor-compliance will be recorded: these patients will be included in ITT analysis, but excluded in 'completers analyses'. The same procedures will be used to obtain the five year follow-up data.

4. Trial procedures

Practices will deliver an VLED phase followed by structured food reintroduction and long term weight loss maintenance. Training for the practice nurses/dietitians in VLED delivery, maintenance diet program and behaviour therapy will be provided by the Boden Collaboration, University of Sydney. Training for the practice nurses/dietitians in the maintenance diet program and behaviour therapy will be provided by Diabetes NSW & ACT. To increase access in regional areas, practices may deliver the intervention via telehealth but all participants will attend their GP practice for safety monitoring and collection of study data.

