5.1 Adverse Event Monitoring

Adverse events

Adverse events are defined as any new medical event or worsening of an existing condition (including a clinically significant laboratory result) with onset after the signing of consent, whether or not the adverse event is deemed related to the study procedures. Participants will be questioned regarding the onset of any adverse events at each appointment in a non leading way (e.g how are you feeling). Participants will also be encouraged at the start of the study to spontaneously report any changes they notice while on the study. The following information will be recorded:

Adverse event term

Note: This should be a diagnosis of the event based on signs, symptoms, and/or other clinical information. In the absence of a diagnosis, the individual signs/symptoms should be documented

- Start date
- Status (resolved/recovered, resolving/recovering, not resolved/recovered, resolved/recovered with sequelae)
- End Date
- Seriousness (serious or not serious)
- Severity (mild, moderate or severe based on impact to daily functioning)
- Relationship to study treatment (definitely related, likely related, possibly related, unlikely related, not related)
- Treatment required (medication, other, none)
- Action taken with study treatment (no change in study treatment, study treatment modified, study treatment stopped)

The adverse events information may be collected and recorded by the dietitian/nurse. If the dietitian/nurse is unsure regarding relatedness and action to be taken with study procedures, they must consult the GP. If the adverse event requires treatment, this must be prescribed by the GP or another appropriately qualified health care professional.

Glycaemia and blood pressure adverse events

Hyper- and hypoglycaemia and low and high blood pressure will be recorded as adverse events using the criteria below:

Hyperglycaemia

Capillary blood glucose >15 mmol/L or HbA1c >9% or >1% change in HbA1c from previous measurement

Hypoglycaemia

Capillary blood glucose < 4 mmol/L

Low blood pressure

Systolic < 110 or diastolic <60

High blood pressure

Systolic >140 or diastolic > 90

Serious Adverse Events

Serious adverse events (SAE) are those which meet any of the following criteria:

- Results in death
- Is life threatening.

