6. STATISTICS AND DATA ANALYSIS

Statistical analyses and data management will be conducted by specialist staff, in accordance with a pre-specified Statistical Analysis Plan, at the Boden Collaboration, University of Sydney.

The Boden Collaboration will build a database (in RedCap) for the DiRECT study. All data will be entered by the 5 x dietitians from the 5 x PHNs. They will be given unique password protected logins. The Boden Collaboration will oversee the data collection and integrity.

Through specific data identifiers, the data from the DiRECT study can then be linked with the Lumos data linkage project administered by the NSW Government, Department of Health.

The main objective of the study is to determine if a VLED and structured weight management program can be instituted as effectively in primary care in Australia as in the original UK DiRECT trial.

Data will be analysed primarily on an intention-to-treat (ITT) basis with last observation carried forward data on weight and diabetes status for subjects who discontinue the formal weight management program. A 'completers analyses' of participants completing the study will also be performed. Trial documentation and data will be retained for at least 15 years after study completion.

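### The Synopsis makes any adverse event a trigger for last observation carried forward, in conflict with Sections 6 and 3.5; read literally, it could override many observed week-52 results, in either direction

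*Protocol*

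**What the plan says.** Three places in the protocol say how the outcome is obtained when a participant's course is disturbed.

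- **Synopsis, Statistical Analysis:** under intention to treat, the latest weight and diabetes status are carried forward in the case of "subjects who discontinue the formal weight management program or experience an adverse event".
- **Section 6:** the same approach, but with "last observation carried forward data on weight and diabetes status for subjects who discontinue the formal weight management program". There is no adverse-event trigger.
- **Section 3.5,** on those who leave the program: "Data analysis will use best available follow-up weights (from routine attendances) and end of study diabetes status for subjects who discontinue". Weight and HbA1c in the GP notes within 3 months either side of the planned 12-month date are accepted.

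The Synopsis row on product and dose adds that the analysis is by intention to treat, "with follow-up data continuing to be collected even if treatment is stopped".

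Section 5.1 takes an adverse event to be "any new medical event or worsening of an existing condition (including a clinically significant laboratory result) with onset after the signing of consent". A relation to study procedures is not required. It also states: "Hyper- and hypoglycaemia and low and high blood pressure will be recorded as adverse events using the criteria below". The criteria are:

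- systolic pressure below 110 or above 140, or diastolic below 60 or above 90;
- capillary glucose below 4 or above 15 mmol/L;
- HbA1c above 9%, or a change in HbA1c of more than 1% from the previous measurement.

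**The concern.** The Synopsis trigger does not require the event to be serious, related, a cause of stopping, or accompanied by a missing week-52 value. It names a class of participants, and Section 5.1 makes that class potentially large. If the rule were applied as worded to someone who attends week 52, a result measured on schedule could give way to an earlier one.

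This bears on the primary endpoint, which is HbA1c below 6.5% at 12 months with diabetes medication stopped for at least the preceding 2 months. The trial has no control arm. Section 6 sets its aim as being as effective as the original UK trial, for which Section 1.1 cites 46% remission at 12 months. A handling rule that moves the single-arm remission rate therefore moves the comparison directly.

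**Working it through.** The protocol gives no expected adverse-event rate, so there is no figure of its own to reproduce. The check has three steps.

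**1. The three rules side by side, for a participant with a week-52 HbA1c**

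| Participant | Synopsis | Section 6 | Section 3.5 |
|---|---|---|---|
| Stays in the program, had an adverse event | carry-forward | observed value | not addressed |
| Discontinues | carry-forward | carry-forward | end-of-study status |

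The Synopsis departs from Section 6 in the first row. Both depart from Section 3.5 in the second.

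**2. How many participants the trigger could reach**

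Appendix A ticks adverse-event monitoring at Appointments 2 to 20, which is 19 occasions. With an assumed probability p of an event at each appointment, independent across appointments, the share with at least one event is 1 − (1 − p)^19:

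- p = 2%: 1 − 0.98^19 = 0.319
- p = 5%: 1 − 0.95^19 = 0.623
- p = 10%: 1 − 0.90^19 = 0.865

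The share passes one half at p = 1 − 0.5^(1/19) = 0.036, or about 3.6% of appointments.

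**3. Which way the result could move**

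Section 4.4 schedules HbA1c at screening and at weeks 13, 25, 37 and 52.

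*Upward.* Suppose HbA1c is 5.6% at week 37 and 6.8% at week 52. The rise of 1.2 points is an adverse event under Section 5.1, and the participant is no longer in remission. Carrying forward the week-37 status would count a remission.

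*Downward.* Suppose a participant has one blood-pressure reading outside the limits at week 5 and is in remission at week 52. The last HbA1c before the event is the screening value, and the entry criteria in Section 3.2 make that diabetic or on treatment. Carrying it forward would count a failure.

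*Net effect in an illustration.* Assume the following:

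- 65% are in remission at week 13 and 46% at week 52, with the 19-point loss spread equally over weeks 25, 37 and 52. Remission is then 65%, 58.7%, 52.3% and 46% at weeks 13, 25, 37 and 52.
- Nobody enters remission after week 13.
- Events are unrelated to glycaemic status.
- The value carried forward is the last HbA1c status before the first event.

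Write q = 1 − p. A first event at Appointments 2–9 has probability 1 − q^8 and carries the screening status (0% remission). A first event at Appointments 10–13 has probability q^8 − q^12 and carries week 13. At Appointments 14–16 the probability is q^12 − q^15, carrying week 25. At Appointments 17–20 it is q^15 − q^19, carrying week 37. Then:

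- Relapsers counted as in remission = (q^8 − q^12)(0.65 − 0.46) + (q^12 − q^15)(0.587 − 0.46) + (q^15 − q^19)(0.523 − 0.46)
- Remitters counted as failures = 0.46(1 − q^8)

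| p | Relapsers counted as in remission | Remitters counted as failures | Analysed rate (true rate 46%) |
|---|---|---|---|
| 2% | 2.2% | 6.9% | 41.3% |
| 5% | 3.9% | 15.5% | 34.4% |
| 10% | 4.2% | 26.2% | 24.0% |

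For p = 5%, 46 + 3.9 − 15.5 = 34.4. Under these assumptions the net movement is downward. If events were concentrated among those who relapse late, the upward part would weigh more. With the adverse-event trigger removed, no observed value is replaced because of an event and the rate stays at 46%.

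**The case against.** The strongest reply is that last observation carried forward fills gaps. If week 52 is observed, it is itself the last observation and nothing is overwritten. No passage says that data after an adverse event are discarded. The Synopsis continues data collection after treatment stops, and Section 3.5 uses end-of-study status even for those who leave the program. On this view the clause loosely describes people lost because of an adverse event. Section 6 also refers to a pre-specified statistical analysis plan, not shown here, which may settle the matter.

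Much of this stands: overwriting an observed week-52 value is one reading of the Synopsis, not the only one. It does not remove the conflict. If the clause meant events that lead to stopping, it would add nothing, because those participants already discontinue. The rule selects by type of participant and never mentions missing data. An analysis plan would still have to choose among protocol statements that disagree.

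A reader might infer three stronger claims that the documents do not support.

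- *Most participants would have their result replaced.* This needs an event rate that the protocol does not give. At 2% of appointments the share is 32%. Out-of-range readings also tend to cluster within people, which lowers the share ever affected.
- *Every relapse would be hidden.* Section 4.1.3 takes diabetes to have returned at HbA1c above 6.5%, whereas the adverse-event criterion needs more than 9% or a change of more than 1%. A rise from 5.8% to 6.6% is a relapse but meets neither HbA1c criterion.
- *The rule favours remission.* Early events work the other way, and in the illustration they dominate.

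**Conclusion.** The concern holds in a limited form. It is certain from the text alone that the Synopsis, Section 6 and Section 3.5 give three different rules for the primary analysis, and that the Synopsis makes an adverse event by itself a trigger for carry-forward.

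The effect on the results is conditional. It requires the literal reading, and its reach depends on assumed, independent event rates: 32% to 86% of participants for 2% to 10% of appointments. The direction is not fixed. In the illustration a true 46% is analysed as 41% to 24%, but that rests on an assumed remission course and on events unrelated to glycaemia, so it shows sensitivity and is not a forecast. Because the trial is judged against an external remission rate, the primary rule should not be left open to this reading.

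**What to change.** 1. Delete the adverse-event limb of the Synopsis sentence (the last five words of "subjects who discontinue the formal weight management program or experience an adverse event").
2. Make the Synopsis, Section 3.5 and Section 6 state one rule. Aligning only the Synopsis with Section 6 would leave both at odds with Section 3.5.
3. State in that rule that an observed week-52 HbA1c and medication status, or the GP-recorded value in the Section 3.5 window, is always used, whatever adverse events or discontinuation occurred. Limit any carry-forward to participants whose week-52 data are missing.

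The cost is a wording amendment to three passages. It needs no new data, changes no visit, and leaves adverse-event recording and clinical care as they are. It should be made before the outcome data are examined.

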10 INTRODUCTION

1.1 **Background: the problem**

T2DM is closely linked to obesity and is the main contributor to the rising costs of obesity.^{1,2} It seldom develops with BMI <21 kg/m² and most affected individuals have BMI >25 kg/m² with about 50% having BMI >30 kg/m^{2,3,4}. At a BMI >35 kg/m², 20% of all men and 11% of women have known diabetes⁵. There is increasing concern about the most rapidly rising categories of severe obesity that demand greater weight loss to control secondary medical consequences. There is overwhelming evidence that modest sustained weight loss, e.g. current target of 5-10%, prevents the onset of most new T2DM in people with pre-diabetes⁶ and it improves *all* aspects of diabetes control (glycaemia, blood pressure, lipids and microvascular damage ⁷ with reductions in drug doses^{8,9}). Advice to lose and maintain 5-10% weight loss, by diet and exercise, is included in most guidelines. However, most patients with T2DM are now managed in primary care, many do not see a dietitian and few achieve even 5% weight loss. Following guidelines, most obese/overweight patients who develop T2DM will be prescribed 4-6 drugs (hypoglycaemic, statin, anti-hypertensives) plus drugs/treatments for other conditions attributable largely to their obesity, e.g. angina, arthritis, gastro-oesophageal reflux, obstructive sleep apnoea and depression. The reduction in coronary heart disease (CHD) risk by this polypharmacy, following current guidelines, has been estimated to be only 5-10%.^{10,11} Compliance with drug treatments is poor¹² in part because some commonly used anti-diabetic and antihypertensive drugs cause further weight gain¹³ and costs are substantial. The prognosis of obesity with T2DM thus remains poor. For a person with diabetes aged between 50 and 60 years, life expectancy is reduced by 6 years.¹⁴ The diagnosis is also stigmatising and brings personal costs through insurance penalties and employment problems.

T2DM is characterised by defects in both insulin sensitivity and beta-cell function. It is commonly perceived as steadily progressive, with an inevitable decline in beta cell function and requirement for insulin therapy after an average of 10 years.^{15,16} However, bariatric surgery has been shown to reverse the metabolic abnormalities of T2DM rapidly at least in patients up to 6 years after diagnosis.¹⁷ The Counterpoint study in Newcastle demonstrated that this benefit can be reproduced by negative energy balance alone, and that the normalisation of fasting plasma glucose persists for up to 3 months after return to normal diet.¹⁸ It is clear that for at least some patients, the beta cells are not permanently damaged but merely metabolically inhibited in T2DM, as previously hypothesised.¹⁵ This proof of principle study reported a dramatically sudden return of fasting blood glucose to normal,

associated with a rapid fall in hepatic fat content to non-diabetic control levels during an 8 week 2510 kJ (600 kcal)/day diet. Observation of beta cell function using a gold-standard method demonstrated the slower, gradual return of normal first phase insulin response over 8 weeks in association with a steady fall in pancreas fat to non-diabetic control levels. The time-course of these observations suggest that the two characteristic defects of T2DM - decreased acute insulin secretion and insulin resistance – are brought about by adverse effects of fatty acids in pancreas and liver respectively. In the DiRECT trial¹⁹ subjects with type 2 diabetes were either treated with a LED (3500 kJ (836 kcal)/day) followed by a structured program to maintain weight loss (intervention arm) or received best practice care (control arm). As expected, there was substantially greater weight loss in the intervention group (10.0 (SD 8.0) vs 1.0 (3.7) kg) and, at 12 months, diabetes remission occurred in 46% of those in the intervention group compared to just 4% in the control arm. Remissions were sustained at 2 years in 36% of those in the intervention group 3% of controls.²⁰ The durability of the remission was related to the extent of sustained weight loss. Similar weight loss with cardiometabolic improvements have been achieved with an LED (3400 kJ), using formula food, in subjects with obesity, again in a primary care setting, in the DROPLET study²¹.

